4.1 Inclusion Criteria

- \geq grade 2 oral mucositis related to chemotherapy for cancer
- Ability to understand and the willingness to review and sign a written informed consent document.
- \geq 18 years of age
- Willingness to use adequate contraception prior to study entry, for the duration of study participation and for 30 days after the last dose for women of child-bearing potential and men

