This study will involve 12 subjects in the first part, plus an additional 3 subjects if a dose-limiting toxicity occurs (see section 2). This sample size is similar to other phase I dose escalation studies and will result in a determination of maximum-tolerated dose. The first objective for the second part (n=46) is to determine whether curcumin decreases an objective measurement of oral mucositis. Mucositis assessment will be conducted by the provider using the WHO scale and CTCAE scale. The scales are continuous between 0 and 4. Analysis of variance will be used to compare the two groups of subjects (standard mouth rinse versus study mouth rinse) separately for each time period (baseline and each week after study mouth rinse initiation). In a one-way ANOVA study, sample sizes of 23, and 23 are obtained from the 2 groups whose means are to be compared. The total sample of 46 subjects achieves 91% power to detect differences among the means versus the alternative of equal means using an F test with a 0.05 significance level. The size of the variation in the means is represented by their standard deviation which is 0.50. The common standard deviation within a group is assumed to be 1.00.

9. Measurement of Effect

Differences between the two mouth rinse groups will be studied with the chi-square test for categorical factors and the analysis of variance F-test for continuous variables with a 0.05 significance level.

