9.1 Determination of objective measurement of oral mucositis

The objective measurements of oral mucositis will be obtained by a health provider's assessment of mucositis. Providers will be uninvolved, trained oncology clinic staff (not affiliated with the study) to reduce bias. Providers will use the Common Terminology Criteria for Adverse Events (CTCAE) Version 4.0 and World Health Organization's (WHO's) Oral Toxicity Scale (OTS). They will be instructed to circle where on the scale they would assess the subject's mucositis level. A baseline evaluation will occur prior to study mouth rinse administration, and then each week after study mouth rinse initiation. The Health Care Provider Assessment Tool is attached as Appendix B.

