9.6 Criteria to be Evaluable for Efficacy and Safety

A subject is evaluable for efficacy (reduction in mucositis) if at least 70% of the study mouth rinse doses were taken as documented on the daily log (Appendix A). Differences between groups in terms of response rate will be evaluated by ANOVA (section 8).

A subject is evaluable for safety (toxicity) if a minimum of one dose of the study mouth rinse was taken.

10. Correlative Studies (Laboratory Studies)

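### Section 8 compares raw weekly mucositis grades between arms without using each subject's own baseline grade, which gives up precision and leaves the result exposed to chance imbalance in entry severity

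*Combined protocol and SAP*

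**What the plan says.** Section 8 sets the aim of the randomised part: "The first objective for the second part (n=46) is to determine whether curcumin decreases an objective measurement of oral mucositis". The analysis is an ANOVA of the two arms, done "separately for each time period (baseline and each week after study mouth rinse initiation". The sample-size statement confirms a one-way model with arm as the only factor: "In a one-way ANOVA study, sample sizes of 23, and 23 are obtained from the 2 groups whose means are to be compared". Section 9 adds a general rule of chi-square tests for categorical factors and F-tests for continuous ones, with no baseline term.

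Section 9.6 opens with "A subject is evaluable for efficacy (reduction in mucositis) if at least 70% of the study mouth rinse doses were taken", and then says "Differences between groups in terms of response rate will be evaluated by ANOVA (section 8". Response is not defined there or elsewhere.

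Entry grade is collected. Section 9.1 says "A baseline evaluation will occur prior to study mouth rinse administration, and then each week after study mouth rinse initiation", on both the CTCAE and WHO scales, which Section 8 treats as continuous from 0 to 4. Section 9.3 also provides a baseline pain score.

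Entry grade can vary. Section 4.1 admits subjects at or above "grade 2 oral mucositis related to chemotherapy for cancer". Section 5 starts the rinse only when mucositis is above grade 2. These two statements conflict and must be reconciled. Under either one, more than one entry grade is possible.

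No section gives a change score, a baseline covariate, a repeated-measures model or stratification of the randomisation by entry grade. Duration (Section 9.4) and the lack-of-activity rule (Section 6.3) are built on reaching grade 0 and do not use entry grade either.

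**The concern.** Subjects may start at different points in the upper part of a five-grade scale, and a subject who starts worse may well be worse a week later. A model with arm alone leaves that variation in the error term, so the arm difference is estimated less precisely than the collected data allow. In one trial with 23 per arm, the arms can also differ by chance in mean entry grade. Part of that difference would then appear in the week 1 and week 2 comparisons, where it could imitate or hide a curcumin effect.

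Testing the arms at baseline does not help. It adjusts nothing, and the plan attaches no action to its result. The 70%-of-doses rule adds to the exposure: it selects the efficacy set after randomisation, so that set need not keep the balance in entry grade that randomisation gives on average.

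**Working it through.** **Inputs from the documents.** 23 per arm, allocated 1:1 (Precis, Sections 3 and 8). Significance level 0.05, F test, within-group SD 1.00, SD of the two group means 0.50, stated power 91% (Section 8). For two means, an SD of 0.50 about their average is a difference of 2 × 0.50 = 1.0 grade.

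**Inputs assumed.** The documents give neither the SD of the baseline grade nor its correlation r with the later grade. Both are shown over ranges.

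**1. The plan's own figure.** Noncentrality = (23/2) × (1.0/1.00)² = 11.5, with 1 and 44 degrees of freedom. Power from the noncentral F = 0.912. The stated 91% reproduces. It refers to the raw grade at one time point with no baseline term.

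**2. Chance imbalance at entry.** The SE of the arm difference in mean baseline grade is SD × √(2/23) = SD × 0.295. The probability of an imbalance of at least 0.25 grade in either direction is 2 × [1 − Φ(0.25/SE)].

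| Assumed baseline SD | SE | 0.25/SE | Probability |
|---|---|---|---|
| 0.4 | 0.118 | 2.12 | 3% |
| 0.5 | 0.147 | 1.70 | 9% |
| 0.7 | 0.206 | 1.21 | 23% |
| 1.0 | 0.295 | 0.85 | 40% |

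If whole grades are recorded and only grades 3 and 4 enter (the Section 5 wording), the SD is at most about 0.5, reached with an even split. If grades 2 to 4 enter (the Section 4.1 wording), an assumed 60/30/10% split over grades 2, 3 and 4 gives 0.67, and an even split between grades 2 and 4 gives 1.0.

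**3. How much of an imbalance reaches the later comparison.** The expected shift is slope × imbalance, with slope = r × (later SD)/(baseline SD). With later SD 1.0, baseline SD 0.7 and an imbalance of 0.25:

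- r = 0.3: (0.3/0.7) × 0.25 = 0.11 grade
- r = 0.5: (0.5/0.7) × 0.25 = 0.18 grade
- r = 0.7: (0.7/0.7) × 0.25 = 0.25 grade

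Against the planned 1.0-grade difference this is about one tenth to one quarter.

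**4. Gain from adjustment.** With baseline grade as covariate, the residual SD is 1.00 × √(1 − r²), the SE is 0.295 × √(1 − r²), and the error degrees of freedom are 43. Power is for the planned 1.0-grade difference.

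| Assumed r | SE | Power |
|---|---|---|
| none (as planned) | 0.295 | 91.2% |
| 0.1 | 0.293 | 91.5% |
| 0.3 | 0.281 | 93.5% |
| 0.5 | 0.255 | 96.9% |
| 0.7 | 0.211 | 99.6% |

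If r were 0, ANCOVA would still give 91.2%, so the lost degree of freedom has no visible cost.

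**5. A plain change score is not a safe substitute.** With equal SDs at baseline and follow-up, its SD is √[2(1 − r)]. Power is then 65.0%, 80.0%, 91.2% and 99.0% at r = 0, 0.3, 0.5 and 0.7. Below r of about 0.5 it does worse than the raw comparison.

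**The case against.** The strongest reply is that nothing is broken. Arms are randomised 1:1, so a test of weekly group means is valid. Raw-grade ANOVA, ANCOVA and a change score all target the same average arm difference. That stands, and the point is about precision and chance imbalance, not bias in expectation.

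A reader might go further and infer that the plan never measures its own objective, because a subject who falls from grade 4 to 2 scores the same that week as one who stays at 2. The scoring is as described, but the inference is not supported. The objective's wording can be read as lower than control, which the weekly contrast addresses. The phrase in Section 9.6, "A subject is evaluable for efficacy (reduction in mucositis", is a parenthesis in a rule about adherence, not an endpoint definition. The clearer gap in Section 9.6 is that response is undefined.

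Nor does an imbalance at entry pass in full to later weeks. Step 3 shows that this happens only at the top of the assumed range.

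The gain may also be small. Entry is confined to the upper part of the scale, and many subjects may reach the floor at grade 0. Both could hold r down, and at r = 0.1 power moves only from 91.2% to 91.5%. At its own planned effect the study is adequately powered without adjustment. Efficacy is also a secondary objective, the primary one being the MTD. These points limit the weight of the concern. They are not a reason to leave a collected baseline value unused.

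**Conclusion.** The point holds as an avoidable loss of precision and an avoidable exposure to chance imbalance in entry severity. It does not show that the comparison is invalid or that the 91% is wrong.

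Its size depends on two quantities that the documents do not give. Over baseline SDs of 0.4 to 1.0, an imbalance of at least 0.25 grade occurs in about 3% to 40% of trials. At an SD of 0.7, such an imbalance shifts the later arm difference by about 0.11 to 0.25 grade for correlations of 0.3 to 0.7. Adjustment takes power from 91.2% to between 91.5% and 99.6% for correlations of 0.1 to 0.7. The calculations treat the grade as continuous, as Section 8 does, and assume that all 23 per arm are analysed. The 70%-of-doses rule could reduce that number and disturb the balance. The plausible baseline SD cannot be narrowed until Sections 4.1 and 5 agree on the entry grade.

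The change should be made because it is nearly free. The trial would remain interpretable without it.

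**What to change.** - **Sections 8, 9 and 9.6:** analyse the post-baseline provider-assessed grade by ANCOVA, with arm and the subject's baseline grade on the same scale (WHO with WHO, CTCAE with CTCAE).
- **Pain:** use the same model, with the baseline pain score as covariate.
- **Baseline:** replace the between-arm significance test with a descriptive table of entry grade and pain by arm.
- **Section 9.6:** define response, or remove the term and refer to the ANCOVA.
- **Sections 4.1 and 5:** reconcile the two statements of the entry grade.

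An unadjusted change score should not be adopted in place of ANCOVA unless a correlation is stated and justified.

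The cost is wording and one error degree of freedom (43 instead of 44). The baseline values are already collected, so no subjects, visits or data are added.

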On day 17 or 18 after the first day of taking the mouth rinse for the study, the subject will be called by a study staff member, who will review and follow up on any side-effects that the subject is experiencing and answer any questions about the study or study mouth rinse. The staff member will remind the subject to complete a subject self-assessment tool (Appendix C) and the daily log (Appendix A) (only if they are still on study mouth rinse) and bring them to the next visit. The phone call will take about 15 minutes.

5.1.8 Visit 5

This visit will occur 7 days (+/- 1 day) after Visit 4. A mucositis assessment (CTAE version 4.0 and WHO Oral Toxicity Scale) will be conducted and documented by a health provider (Appendix B), who will review and follow up on any side-effects that the subject is experiencing and obtain the daily log (Appendix A) from the subject (if the subject is still on study mouth rinse). A blood sample will be obtained to assess liver function (CMP) and clotting function (PT and INR). A blood and saliva sample will be obtained for research purposes (section 10). If the mucositis score \leq Grade 2 but is unresolved, then the subject will continue to receive the study treatment (curcumin or standard mouth rinse) until the mucositis is resolved (Grade 0). Sufficient mouth rinse will be given to the subject for the subsequent week of the study. This visit will take approximately 30 minutes.

5.1.9 Weekly phone calls to subjects receiving study mouth rinse (curcumin or standard mouth rinse)

Between each visit, each subject will be called by a study staff member, who will review and follow up on any side-effects that the subject is experiencing and answer any questions about the study or study mouth rinse. The staff member will remind the subject to complete a subject self-assessment tool (Appendix C) and the daily log (Appendix A) and bring them to the next visit. The phone call will take about 15 minutes.

5.1.10 Weekly visits for subjects receiving study mouth rinse (curcumin or standard mouth rinse)

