5.2 Study Calendar

Study Procedure	Visit 1 (Screening)	Week 1		Week 2		Week 3		Week 4- mucositis resolution		Final visit
	day -1	Visit 2: day 0	Phone call 1: day 3	Visit 3: day 7	Phone call 2: day 10	Visit 4: day 14	Phone call 3: day 17	Visit: For phase II: weekly cycle repeated until mucositis is resolved (and no AEs)	Phone calls	
activity window		At or w/in 48hr of Visit 1	+ 1 day	+/- 1 day	+ 1 day	+/- 1 day	+ 1 day	+/- 1 day	+ 1 day	+/- 1 day
Sign Informed Consent	X									
Oral exam for hygiene	X									
Pregnancy test	X ¹									
Provider mucositis assessment ²	X	X ³		X		X		X ^a		X
Provider supplies study mouth rinse		X		X		X ^a		X ^a		X
Provider supplies study journal, self-assessment		X		X		X ^a		X ^a		X
Provider collects journal and self-assessments				X		X		X ^a		X
Remind subject to complete self-assessment		X	X		X		X		X ^a	
Blood collection for liver function (CMP) ⁴	X			X		X		X ^a		X
Blood collection for clotting (PT and INR) ⁴	X			X		X		X ^a		X
Research blood collection ⁵		X		X		X		X ^a		
Research saliva collection ⁵		X		X		X		X ^a		
Collect AEs			X	X	X	X	X	X ^a	X ^a	X
Review of concomitant medications	X	X		X		X		X ^a		X

¹ Blood or urine pregnancy test, if not already done as part of standard of care

² Includes CTAE version 4.0 and WHO oral Toxicity scale.

³ Mucositis assessment at Visit 2, only if a different day than Visit 1 (does not need to be repeated if Visit 1 and 2 are done on the same day)

⁴ Does not need to be repeated if already done for standard of care.

⁵ 6 ml of peripheral blood into a non-anti-coagulated tube, 2 ml saliva into a sterile tube; processed and stored as described in the operations manual.

^a Only if subject is still taking study mouth rinse based on improvement of mucositis at each visit, beginning at visit 4.

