5.6 Determination of MTD

The MTD will be determined as follows: If a DLT occurs in any one of the 3 patients at a specific dose level, an additional 3 patients must be treated at that dose level to achieve statistical validity of the MTD. If 2 of the 6 patients (17%) at a dose level develop a DLT, the previous dose level will be used as the MTD. If no DLT is observed, then the MTD will be the highest dose. To ensure safety of subjects at each dose level, all assessments will be completed at Visit 5 for subjects at a dose level before another subject is given study drug at the

subsequent dose level.

6. Expected Adverse Events

Toxicities will be graded by health care providers using the Common Terminology Criteria for Adverse Events (CTCAE) Version 4.0 weekly after initiation of study mouth rinse until mucositis is resolved (Grade 0) (see Provider Assessment in calendar, section 5.2). Toxicities will be assessed by subject self-evaluation during study mouth rinse administration between clinic visits (see Subject Assessment in calendar, section 5.2).

Very few studies have reported any severe or serious side effects from curcumin and most studies have involved oral administration of curcumin. No major toxicity has been found in studies where curcumin is used short-term. Increased bleeding may occur due to inhibition of platelet aggregation (very rare). Possible other side effects associated with curcumin include: vomiting, nausea, rash and GI distress. In a study of subjects with colon cancer, oral curcumin at doses ranging from 0.45 to 3.6 gram/day for 1 to 4 months was associated with nausea and diarrhea and caused an increase in serum alkaline phosphatase and lactate dehydrogenase[15]. In one study of patients with advanced pancreatic cancer, 5 of the 17 patients receiving oral curcumin (8 gram/day) in combination with gemcitabine reported intractable abdominal pain after a few days to 2 weeks of curcumin intake[16]. In a recent study of topical curcumin for mucositis in juveniles and children[14], there were no oral adverse events documented and no systemic adverse events that possibly could be related to the use of the curcumin mouthwash.

Patients will receive full supportive care as appropriate. The rationale for treatment, dosage and the date of treatment will be recorded in the medical record.

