6.3 Criteria for Study Discontinuation

If 2 patients develop a DLT at dose 1, then the trial will be closed due to unacceptable toxicity. If any patient has Grade V toxicity, then, the trial will be placed on immediate hold until the protocol investigators, the sponsor of the IND, the IRB and the FDA have been notified and a determination has been made as to the re-opening of this trial.

If < 5 of the first 10 subjects in the curcumin arm of the second part of the study have Grade 0 mucositis (CTAE version 4.0 and WHO Oral Toxicity Scale) at Visit 4, then the study will be discontinued due to lack of activity.

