9.5 Determination of toxicity profile

Toxicities will be graded by health care providers using the Common Terminology Criteria for Adverse Events (CTCAE) Version 4.0. A baseline evaluation will occur prior to study mouth rinse administration, and then weekly during study mouth rinse administration. Data will be recorded and entered into a database.

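### Section 8 tests mucositis grade between arms at every week, but from day 28 only subjects still on rinse have a scheduled grade, so those late tests are selected on the outcome

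*Combined protocol and SAP*

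**What the plan says.** **Analysis.** Section 8 introduces the efficacy comparison thus: "The first objective for the second part (n=46) is to determine whether curcumin decreases an objective measurement of oral mucositis". The test is a between-arm ANOVA of WHO and CTCAE grade, run "separately for each time period (baseline and each week after study mouth rinse initiation". No final or primary week is named. Section 9.1 describes the same provider grading as weekly after initiation and attaches no condition.

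**Who is graded, and when.**
- Visits 3 and 4 (days 7 and 14) grade every subject.
- After Visit 4, rinse continues only while mucositis is unresolved and at Grade 2 or below (Section 3 and 5.1.6). Section 6.2 removes subjects who have not improved after 14 days.
- Visit 5 (day 21), in the text of 5.1.8, grades everyone. Only the log depends on rinse: staff are to "obtain the daily log (Appendix A) from the subject (if the subject is still on study mouth rinse".
- Later visits fall under 5.1.10, headed "Weekly visits for subjects receiving study mouth rinse (curcumin or standard mouth rinse".
- Toxicity grading follows the same pattern: "weekly after initiation of study mouth rinse until mucositis is resolved (Grade 0" in Section 6, and "then weekly during study mouth rinse administration" in 9.5.
- In the 5.2 calendar, the provider assessment in the column after day 14 carries footnote a: "Only if subject is still taking study mouth rinse based on improvement of mucositis at each visit, beginning at visit 4". The calendar also has a Final visit with a grade but no study day.

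**Rules for absent grades.** Sections 8 and 9 give none for healed or removed subjects. Section 9.6 sets only a threshold of 70% of doses taken.

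**The concern.** A subject who heals leaves the weekly schedule because of the value being compared. If curcumin heals more subjects, more curcumin subjects leave, and those left are the ones who responded least. At the other end, subjects above Grade 2 or removed for non-improvement also leave, and they come mostly from the worse arm. The day-28 and later tests then compare two remnants that are no longer the randomised groups.

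The loss would not be marginal. Section 6.3 stops the study if fewer than "5 of the first 10 subjects in the curcumin arm of the second part of the study have Grade 0 mucositis" at Visit 4. So if Part 2 continues, at least half of those ten have healed by day 14 and, barring relapse and renewed rinse, have no scheduled day-28 grade.

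Because grade is the first objective of Part 2 and the plan ranks no week above another, a null or reversed late-week result could be read as evidence against a benefit that was real.

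**Working it through.** **1. The plan's own figure.** Inputs from Section 8: 23 + 23 subjects, SD of the means 0.50 (a 1.0-grade difference between two arms), within-group SD 1.00, alpha 0.05. Noncentrality = 46 × (0.50/1.00)² = 11.5 with 1 and 44 df, giving power 0.912. The stated 91% reproduces, and it needs all 46 subjects graded at the week tested.

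**2. Loss of numbers alone.** Keep the 1.0-grade difference and assume healed shares (the documents give none). With 30% of control and 50% of curcumin healed, 16 + 12 remain and power is 0.71. With 50% and 80%, 12 + 5 remain and power is 0.42.

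**3. Selection alone.** Assume 30% of control and 60% of curcumin healed, with mean grade 1.5 among the unhealed in both arms. Over all subjects the means are 1.5 × 0.70 = 1.05 and 1.5 × 0.40 = 0.60, a difference of 0.45. Among those still attending the difference is 0.

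**4. Both together, by simulation.** Anchors from the documents: the 6.3 boundary (50% of curcumin at Grade 0 on day 14) and the Section 8 difference and SD. Assumptions:
- A normal latent grade is rounded to 0-4, so Grade 0 means a latent value below 0.5.
- Day-14 latent means are 1.5 (control) and 0.5 (curcumin), with a fall of 0.5 grade per week.
- Correlation between weeks is 0.5 or 0.7, autoregressive or exchangeable.
- There are 20,000 trials per setting.

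Healed at day 14: Φ(−1) = 15.9% of control and Φ(0) = 50% of curcumin. That leaves 23 × 0.841 = 19.4 and 23 × 0.5 = 11.5 unhealed.

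Day 28, latent benefit sustained at 1.0:
- All graded: difference 0.50 (compressed because many grades sit at 0), power 0.74-0.75.
- Subjects healed at day 14 or 21 out: about 15 vs 5-6 remain, difference 0.42-0.47, power 0.15-0.17. A repeat run reached 0.19.
- Subjects above Grade 2 at either visit also out (a proxy for the rinse limit and 6.2): about 10-11 vs 5 remain, power about 0.10.

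Day 28, latent benefit waning to 0.25:
- All graded: difference 0.16, power 0.11.
- Healed out: about 15 vs 8-9 remain, difference −0.08 to 0.06, rejection 0.05-0.06.
- Above Grade 2 also out: rejection 0.05-0.10. At exchangeable correlation 0.7 it is about 0.09 with a mean difference of about −0.2, so most of these rejections favour the standard rinse.

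Day 21, only if sites follow footnote a, healed out:
- Sustained benefit: difference 0.56-0.61 against 0.69, power 0.40-0.45 against 0.82-0.83.
- Benefit waning to 0.5: difference 0.14-0.22 against 0.39, power 0.06-0.09 against 0.32-0.33.

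**The case against.** The strongest reply is that little depends on these tests. The MTD is the primary objective, planned treatment lasts 14 days, the only efficacy decision rule uses Visit 4, and 9.4 healing time already captures late benefit. That stands, and it limits the size of the point.

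A second reply is that 9.1 asks for weekly grading without condition and that the Final visit carries a grade. This shows the documents are inconsistent, but neither provision gives a healed subject a scheduled day-28 grade. Section 9.1 creates no visit, and the Final visit has no day. For a subject healed at Visit 4, Visit 5 might serve as the Final visit, which would cover day 21 but not day 28.

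Day 21 is properly a conflict between text and calendar. Section 5.1.8 grades everyone, 5.6 requires completed Visit 5 assessments in Part 1, and the calendar's column alignment is uncertain in the extracted text. I do not treat loss at day 21 as established.

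The group graded at day 28 is also not simply the unhealed. A subject who heals during the preceding week is graded 0 at that visit and then leaves.

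Finally, the weekly fall, correlation, control mean and rounding are assumptions, and 50% is a stopping boundary rather than an expected healing rate. In the sustained case with only healed subjects out, the difference barely moves (0.42-0.47 against 0.50), so the damage there is mainly lost sample size.

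**Conclusion.** The point holds for the weeks from day 28. Followed as written, the plan tests grade in groups selected on earlier grade, with no rule for the absent subjects. For a sustained benefit, day-28 power falls from about 0.75 to 0.15-0.19, or to about 0.10 once subjects above Grade 2 are also out. A waning benefit can disappear or change sign, with wrong-direction rejections up to about 0.09. These sizes rest on the assumptions in the simulation. That grading becomes conditional on rinse rests on the text alone.

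A reader might infer that the main efficacy comparison or its 91% power is compromised. The documents do not support that: everyone has a scheduled grade at days 7 and 14, and non-improvers are removed only after 14 days. The MTD and 9.4 healing time are also untouched.

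A reader might also infer a bias toward claiming that curcumin works. The pull runs the other way, toward no difference or, in some settings, toward the standard rinse. The consequence is confined to secondary extension-week tests. It is worth correcting because the correction is cheap.

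**What to change.** **Section 8.** State that formal between-arm tests of grade are made at days 7 and 14 only, in the 9.6 evaluable set. Report later weeks descriptively, with the number graded in each arm at each week, and use 9.4 healing time for late benefit.

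**Section 5.2.** Add a separate Visit 5 (day 21) column with grading, adverse events and laboratory tests not conditional on rinse, as 5.1.8 and 5.6 already require. Leave the repeating weekly column conditional. This also makes the Part 1 escalation gate visible for a subject healed by day 14.

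**Not recommended.** Entering healed subjects at Grade 0 and carrying the last grade forward for removed subjects would keep late-week tests and, in simulation, holds type I error at about 0.05. But it overstates the day-28 difference: 0.72-0.79 against 0.50 when benefit is sustained, and 0.48-0.61 against 0.16 when it wanes.

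**Cost.** A short change to the analysis text and one calendar column, with no visits beyond those in 5.1.8. The trial gives up any formal grade test after day 14.
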